2.4. Dose Adjustment/Modifications

Dose modifications are not permitted for subjects in this study.

3. General Statistical Considerations

Continuous variables will be summarized using n, mean, standard deviation, median, 25th percentile (Q1), 75th percentile (Q3), minimum, and maximum values. The precision for continuous variables will be based on the precision of the data itself. The mean, median, 25th percentile, and 75th percentile will be presented to one more significant figure than the original results; the SD will be presented to two more significant figures than the original results; the minimum and maximum will be presented to the same level of precision as the original results.

Categorical variables will be summarized using frequency counts and percentages. Percentages will be presented to 1 decimal place. If the count is 0, the percentage will not be displayed. If the count equals the denominator, the percentage will be displayed as 100.

When **count data** are presented, the percentage will be suppressed when the count is zero to draw attention to the non-zero counts. A row denoted “Missing” will be included in count tabulations as needed to account for dropouts and missing values. The denominator for all percentages will be the number of subjects in the treatment group within the analysis set of interest, unless otherwise specified.

Baseline, unless otherwise specified, will be defined as the last non-missing measurement collected prior to dosing on the same date as the first dose of study treatment; if it is not available, the first measurement up to 2 hours post first dose of study treatment will be used. For

subjects who are randomized, but not treated, the baseline will be defined as the last non-missing measurement on or before the date of randomization. For height, weight and body mass index baseline will be defined as the last non-missing measurement collected on or before the date of the first dose of study treatment (without consideration of time). .

Study Day 1 is the calendar day that the first dose of the study treatment is administered. Subsequent study days are calculated as the date of assessment/event – date of the first dose + 1. If a subject is not treated, the date of randomization is used to define study day rather than the date of first dose. For assessments or events that occur before the first dose date, study day is calculated as the date of interest minus the first dose date.

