3.4.4. Per Protocol (PP)

The Per Protocol (PP) Population includes all subjects in the ITT-c Population who do not have any protocol deviations that may unduly influence the primary efficacy outcomes as assessed by the sponsor prior to unblinding ([Section 4.2](#)) and do not meet any of the criteria shown below.

1. Compliance rate <80% ([Section 6.4.1. Extent of Treatment Exposure and Compliance](#))
2. Do not complete Day 33 Visit (discontinuation from study prior to Day 33 or incomplete follow-up at the time of analysis)

The reasons for exclusion from the PP Population will be summarized by treatment group and listed using the ITT-c Population.

Subjects will be analyzed in the treatment group that corresponds to the study treatment received during the study.

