7.4. Electrocardiogram

All Electrocardiogram (ECG) results will be summarized by treatment group and visit in the Safety population and a listing will be presented of all results with abnormalities flagged.

8. Efficacy Analysis

Unless otherwise specified, efficacy analyses will be performed using ITT-c population and the following methods will be implemented:

For time to event endpoints time and date will be used and 24 hours will be considered as a day. Descriptive statistics using the Kaplan-Meier method will include the median, 25th percentile, and 95% CIs (log-negative-log transformation). Additionally, the cumulative event rate (SE) will be summarized by treatment group and presented graphically over time. For between group comparisons, Cox Proportional Hazards models (tie handling will be addressed first using the exact method then with Efron's method if the exact method does not converge) will include treatment group, randomization stratification factors of age (≤ 50 years or 51 to 64 years) and duration of COVID-19 symptoms (≤ 3 days or >3 days and ≤ 5 days), and the baseline value of the endpoint. The hazard ratios with associated 95% CIs (Wald) and p-values (analysis of maximum likelihood estimates) comparing EDP 235 [REDACTED] versus Placebo, and EDP 235 [REDACTED] versus Placebo will be reported. Model assumptions will be checked via a log-negative-log plot and/or Schoenfeld residuals as appropriate. Subjects who do not achieve the specified endpoint will be censored with time imputed as treatment start time as follows:

COVID-19 diary:

- Subjects who have not been followed through the Day 33 visit (discontinuation from study or incomplete follow-up at the time of analysis) or completed Day 33 diary will be censored at Day 33.

Other time to event endpoints:

- Subjects who discontinued from the study will be censored at Day 33.
- Subjects who have completed the Day 33 visit will be censored at Day 33 Visit Date.

For treatment comparisons of change from baseline endpoints, analysis of covariance (ANCOVA) models will include treatment group, randomization stratification factors of age (≤ 50 years or 51 to 64 years) and duration of COVID-19 symptoms (≤ 3 days or >3 days and ≤ 5 days) and baseline value of the endpoint as the covariate. The least-squares means, SE, and 95% CIs will be presented for individual groups and the difference between groups. The p-value for

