8.1.1. Primary Analyses

8.1.1.1. Time to Improvement of Targeted COVID-19 Signs/Symptoms using the COVID-19 Symptom Diary through Day 33

Improvement of targeted COVID-19 signs/symptoms is defined by the following the event occurring on the first of 2 consecutive days or on Day 33 when the following criteria are met:

- All symptoms scored as mild, moderate or severe at baseline are scored as mild or absent
- All symptoms scored as absent at baseline are scored as absent

Time to improvement of targeted COVID-19 signs/symptoms through Day 33 will be summarized graphically using Kaplan-Meier plots and analyzed by the Cox proportional hazard model as described in [Section 8](#).

8.1.1.2. Time to SARS-CoV-2 RNA Viral Load TND Assessed by RT-qPCR through Day 33

Time to SARS-CoV-2 RNA to TND is defined as the time between the date of the first dose to the first date of achieving viral load TND.

Time to SARS-CoV-2 RNA TND will be analyzed as described in [Section 8](#).

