8.2. Secondary Efficacy Endpoints

8.2.1. Proportion of Subjects with Targeted COVID-19 Signs/Symptom Improvement using the COVID-19 Symptom Diary through Day 33

The proportion of subjects demonstrating targeted COVID-19 signs/symptoms improvement through Day 33 will be summarized overall and by treatment group and CMH methods applied as described in [Section 8](#).

8.2.2. Change from Baseline in Targeted COVID-19 Signs/Symptom Total Score using the COVID-19 Symptom Diary through Day 33

Change from baseline in targeted COVID-19 signs/symptoms will be summarized for the total mean score and analyzed using the methods described in [Section 8](#).

Additionally, the 14 individual symptom scores will be summarized descriptively by study visit for each treatment group.

8.2.3. Proportion of Subjects with Medically Attended Visits for COVID-19 Through Day 33

The proportion of subjects with medically attended visits for COVID-19 through Day 33 will be summarized by treatment group and will be analyzed using the same CMH methods as described in [Section 8](#).

8.2.4. Proportion of Subjects Requiring Hospitalization (Defined as ≥ 24 Hours of Acute Care) for COVID-19 Through Day 33

The proportion of subjects requiring hospitalization for COVID-19 through Day 33 will be summarized by treatment group by treatment group and will be analyzed using the same CMH methods as described in [Section 8](#).

8.2.5. Proportion of Subjects who Require Hospitalization and Mechanical Ventilation (Invasive and Non-Invasive) Through Day 33

The proportion of subjects who require hospitalization and mechanical ventilation through Day 33 will be summarized by treatment group and will be analyzed using the same CMH methods as described in [Section 8](#).

8.2.6. Proportion of Subjects with COVID-19 Related Events or All-Cause Mortality Through Day 33

COVID-19 related events include complications based on the investigator's assessment, medically attended visits, hospitalizations, intensive care unit (ICU) admissions, requirement for supplemental oxygen or increased in supplemental oxygen requirement, requirement for mechanical ventilation (invasive and non-invasive) or all-cause mortality. The proportion of subjects with COVID-19 related events or all-cause mortality through Day 33 will be summarized by treatment group and will be analyzed using the same CMH methods as described in [Section 8](#).

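### Event-free subjects not observed to Day 33 are censored at Day 33, so unobserved time is counted as time without improvement or clearance

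*SAP*

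**What the plan says.** The rules are in SAP Section 8, Efficacy Analysis, and apply to subjects who do not reach the endpoint.

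- **COVID-19 diary.** "Subjects who have not been followed through the Day 33 visit (discontinuation from study or incomplete follow-up at the time of analysis") are censored at Day 33, together with subjects who completed the Day 33 diary.
- **Other time-to-event endpoints.** "Subjects who discontinued from the study will be censored at Day 33". For completers: "Subjects who have completed the Day 33 visit will be censored at Day 33 Visit Date". There is no visible rule for a subject still in follow-up at the analysis.

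The lead-in to these rules, about imputing the time as the treatment start time, is awkward. Read with the bullets, it fixes the clock time on the censoring date and leaves the date at Day 33.

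Both primary efficacy endpoints, time to symptom improvement and time to undetectable RNA, are analysed by these methods (Sections 8.1 and 8.1.1). The only planned sensitivity analysis repeats them in the Per Protocol (PP) population (Section 8.1.2).

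**The concern.** Censoring should mark the point at which information on a subject ends. Under this rule, a subject last seen without improvement on Day 5 stays in the risk set to Day 33, which adds 33 − 5 = 28 days that nobody observed. ITT-c requires only one post-baseline primary efficacy measurement (Section 3.4.3), so such subjects are in the main analysis.

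For discontinued subjects the rule amounts to imputing discontinuation as not improved. That can be a legitimate estimand, but the SAP does not state it and calls it censoring. For a diary subject merely still in follow-up, the rule has no visible rationale: that subject has not failed and is only not yet observed.

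At stake are the Kaplan-Meier rates and medians, and the hazard ratios of each EDP 235 dose against placebo. Unequal dropout can move a hazard ratio in either direction, and more dropout on placebo favours active.

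**Working it through.** The visible SAP gives no dropout rate, arm size or event count, so there is no stated figure to reproduce. What follows illustrates the mechanism and its possible size.

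**Small example.** Take ten subjects with events on Days 4, 6, 8, 10 and 12, one lost event-free on Day 5, and four event-free at Day 33.

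- Censored at last contact: S = 9/10 × 7/8 × 6/7 × 5/6 × 4/5 = 0.45, a cumulative event rate of 55%.
- Current rule: the lost subject stays at risk, so S = 5/10 = 0.50, a rate of 50%.

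**Assumptions for the larger calculation.** Event times are exponential with placebo median 9 days, so λ = ln 2/9 = 0.0770 per day. The true hazard ratio is 1.00 or 1.40 (above 1 favours active). Dropout is unrelated to outcome and uniform over Days 1-20 or Days 1-33. The Cox model has two arms and treatment only. The event is treated as continuously observed, which suits the diary better than undetectable RNA, seen only on swab days.

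**Formula.** Let f_j(t) be the density of observed events in arm j, that is, the event density times the probability of still being observed. The large-sample log hazard ratio β solves

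∫₀³³ { f₁ − (f₀ + f₁) · e^β Y₁ / (Y₀ + e^β Y₁) } dt = 0.

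Under last-contact censoring, Y_j(t) is the probability of being event-free and still observed. Under the current rule, Y_j(t) = 1 − ∫₀ᵗ f_j, because an event-free leaver never leaves the risk set.

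**Hazard ratio under the current rule**

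| Dropout, placebo/active | True 1.00: Days 1-20 | True 1.00: Days 1-33 | True 1.40: Days 1-20 | True 1.40: Days 1-33 |
|---|---|---|---|---|
| 2%/2% | 1.00 | 1.00 | 1.39 | 1.39 |
| 5%/5% | 1.00 | 1.00 | 1.38 | 1.38 |
| 3%/5% | 0.98 | 0.99 | 1.35 | 1.37 |
| 5%/10% | 0.95 | 0.97 | 1.30 | 1.34 |
| 5%/15% | 0.91 | 0.94 | 1.24 | 1.29 |
| 15%/5% | 1.10 | 1.06 | 1.49 | 1.46 |

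Last-contact censoring returns 1.00 and 1.40 in every row.

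**Type I error**, simulated with an assumed 75 per arm (10,000 replicates, two-sided Wald 5%, Monte Carlo SE at most 0.3 points):

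| Dropout, placebo/active | Days 1-20 | Days 1-33 |
|---|---|---|
| 3%/5% | 5.1% | 4.9% |
| 5%/10% | 5.9% | 5.5% |
| 5%/15% | 8.3% | 6.5% |
| 15%/5% | 7.9% | 6.0% |

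At 15%/5%, 7.2 of the 7.9 points (5.1 of the 6.0) favour active. Last-contact censoring stays at 4.6-5.4%.

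**Subjects merely still in follow-up**, equal in both arms, with observation ending uniformly over Days 1-33. The true placebo event rate at Day 33 is 1 − e^(−33λ) = 92.1%. Among subjects cut off early, the share with an observed event is 1 − (e^(−λ) − e^(−33λ))/(32λ) = 1 − 0.344 = 65.6%. The current rule therefore reports:

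- 10% cut off: 0.9 × 92.1% + 0.1 × 65.6% = 89%, median 9.1 days; a true 1.40 becomes 1.37.
- 20% cut off: 0.8 × 92.1% + 0.2 × 65.6% = 87%, median 9.3 days; a true 1.40 becomes 1.35.

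The null stays at 1.00 in both.

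**Dropout that depends on outcome.** Here only subjects with event time beyond 15 days leave, uniformly over Days 1-15. PP-type means all leavers removed.

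| Dropout, placebo/active | True HR | Current rule | Last contact | PP-type |
|---|---|---|---|---|
| 5%/15% | 1.00 | 0.88 | 1.08 | 1.19 |
| 5%/15% | 1.40 | 1.14 | 1.61 | 1.87 |
| 15%/5% | 1.00 | 1.13 | 0.92 | 0.84 |

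No rule is unbiased in this setting.

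**The case against.** **It is a choice of estimand.** For discontinued subjects the rule is explicit and pre-specified, and it agrees with the companion endpoint in Section 8.2.1: "The proportion of subjects demonstrating targeted COVID-19 signs/symptoms improvement through Day 33 will be summarized overall and by treatment group", where by the Section 3 default "The denominator for all percentages will be the number of subjects in the treatment group within the analysis set of interest". Under the rule, the Kaplan-Meier rate at Day 33 equals the proportion observed to improve. This stands as a reason to keep the analysis under its proper name. It does not justify leaving the rule unstated, and it does not cover subjects still in follow-up.

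**Last-contact censoring is not safe either.** This is correct. With outcome-related dropout at 5%/15% it errs in favour of active. Both analyses are therefore needed.

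**The PP analysis already checks the rule.** In part. PP excludes subjects who "Do not complete Day 33 Visit (discontinuation from study prior to Day 33 or incomplete follow-up at the time of analysis"), and with dropout unrelated to outcome, removing non-completers recovers 1.00 and 1.40. In the outcome-related cases the current rule and the PP-type result lie on either side of the truth, so a wide gap between them would be a warning. But PP also removes subjects for protocol deviations and "Compliance rate <80"%, and analyses by treatment received. A difference from ITT-c could not be attributed to the censoring rule.

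**The still-in-follow-up case may be empty.** If the efficacy analysis takes place after the last Day 33 visit, nobody is affected. The visible text does not settle this and parts of the SAP are redacted, but the diary rule itself provides for the case.

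**The consequences are limited.** Also correct. The effect is small with low, balanced dropout. Stopping treatment alone does not trigger the rule, because such subjects continue follow-up (Appendix 14.1, note e). Table 1 lists both endpoints as secondary, there is no multiplicity control, and the primary objective of this Phase 2 trial is safety.

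**Conclusion.** The concern holds and should be fixed. On its plain reading, Section 8 counts unobserved time as event-free in both primary efficacy analyses, and no other visible section corrects this.

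With dropout unrelated to outcome, event rates are too low and medians slightly too long. Equal loss pulls a true effect toward 1 and leaves the null at 1. Unequal loss shifts the hazard ratio either way: by about 0.06 to 0.10 at the null for a 10-point imbalance, and by 0.01 to 0.02 with an imbalance of 3% against 5%.

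The reading of the text is certain. The sizes are not, because they rest on assumed dropout rates, an assumed 9-day placebo median, exponential times and, for type I error, an assumed 75 per arm.

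**What to change.** 1. Censor every event-free subject, discontinued or still in follow-up, at the last time known to be event-free: the last evaluable diary entry, or the last evaluable nasopharyngeal swab or other sample for that endpoint. Keep Day 33 censoring for subjects actually observed to Day 33.
2. The diary event is defined as "the event occurring on the first of 2 consecutive days or on Day 33 when the following criteria are met". State in advance how a final qualifying entry with no second day is handled.
3. Add the missing rule for subjects still in follow-up on the other time-to-event endpoints.
4. Keep the present rule for discontinued subjects as a sensitivity analysis in ITT-c, labelled as discontinuation counted as not improved (or not cleared), because last-contact censoring is itself biased if dropout depends on outcome.
5. Reword the lead-in so that it clearly concerns the clock time only.

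The cost is SAP wording and one derivation in the time-to-event dataset. No new data are needed: the diary is daily, swabs are dated, and subjects who leave early are asked back for end-of-follow-up procedures (Appendix 14.1, note e).

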2.1. Overall Study Design and Plan

This is a randomized, double-blind, placebo-controlled, parallel group, multi-site study in non-hospitalized adult subjects who test positive for SARS-CoV-2 and have COVID-19 symptom onset within 5 days of randomization and who are not at high risk for progression to severe COVID-19. Subjects can be vaccinated or unvaccinated for COVID-19. Subjects with prior COVID-19 infection <90 days before enrollment and/or who received a COVID-19 vaccine dose <90 days before enrollment are excluded from trial participation.

[figure not shown]
Subjects will be randomized in a 1:1:1 ratio to receive either EDP 235 [REDACTED], EDP 235 [REDACTED], or placebo orally once daily for 5 days. Randomization will be stratified by age (≤ 50 years or 51 to 64 years) and by the duration of COVID-19 symptoms (≤ 3 days or >3 days and ≤ 5 days).

The study includes 4 periods:

- Screening period will occur from Day -1 to Day 1. Screening should be completed as soon as possible, and the subject will be randomized within 24 hours of signing the ICF. A subject will be considered enrolled at the time of randomization.
- Treatment period will begin with the first dose of study treatment on Day 1 and will conclude with the end-of-treatment (EOT) visit on Day 5.
- Follow-up period will begin following the last dose of study treatment and will conclude at the end of follow-up (EOFU) visit on Day 33 (28 days after the last dose of study treatment).
- Long-term follow-up period (LTFU) will begin at Day 34 and concludes at the end-of-study (EOS) visit at Week 24.

An overview of the study design is shown in **Figure 1**. Study site visits and assessments are detailed in the Schedule of Study Procedures ([Appendix 14.1](#)).

Figure 1: Study Design

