3.1. Incomplete and Missing Data

Imputation rules for missing dates of prior/concomitant medications, including COVID-19 vaccinations and prohibited medications, and procedures are provided in [Appendix 14.5](#).

Imputation rules for missing AE data are provided in [Appendix 14.5](#).

Data that are continuous in nature but are reported in the form $<x$, $>x$, $\leq x$, or $\geq x$ (where x is considered as the limit of quantitation) will be set to limit of quantitation value with the following exceptions:

- Efficacy endpoint data will be imputed as detailed in [Appendix 14.5](#).
- PK concentrations data will be imputed as detailed in [Appendix 14.5](#).

- Other incomplete/missing data will not be imputed, unless specified otherwise.

All analyses will be conducted using SAS Version 9.4 or higher. Unless otherwise stated, a two-sided test will be used at a significance level (alpha) of 0.05 for all analyses. Two-sided 95% confidence intervals (CI) will be provided when appropriate.

Summary Tables and Figures will be presented by treatment group and will be labelled as follows:

- “EDP 235 [REDACTED]”
- “EDP 235 [REDACTED]”
- “Placebo”

All subject data will be presented in individual subject data listings. Dates will be shown in subject listings as they have been recorded. Unless otherwise stated, unscheduled visit results will be included in date/time chronological order, within subject listings only. All listings will be sorted by subject number, date/time and visit. The treatment group (randomized) as well as subject’s sex and age will be stated on each listing. Unless otherwise stated, data listings will be based on all subjects randomized.

When no data are available for a table or listing, an empty page with the title will be produced with suitable text (e.g., “There are no records for this table/listing.”). For analyses where convergence or the analysis cannot be performed, “NC” (not calculable) will be presented in summary tables.

For the reporting of this study both CDISC SDTM (SDTM Implementation Guide version 3.3 or later) and ADaM (ADaM Implementation Guide version 1.3 or later) standards will be applied.

[REDACTED]

[REDACTED]

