the difference between groups will also be presented. In addition, a two-sample t-test will be used to compare change from baseline between treatment without covariate adjustment (unadjusted mean difference). The p-value for the difference between groups will also be presented under the pooled test (equal variances assumption). Line graphs for both the adjusted and unadjusted means with corresponding 95% CIs will also be generated for secondary efficacy endpoints.

Proportional endpoints will be summarized by treatment group. A 2x2x2x2x2 Cochran-Mantel-Haenszel (CMH) test will be used to test the association treatment group (EDP 235 [REDACTED] versus Placebo) and the endpoint analyzed while taking into account randomization stratification factors of age (≤ 50 years or 51 to 64 years) and duration of COVID-19 symptoms (≤ 3 days or >3 days and ≤ 5 days). In addition to the p-value, the risk differences and associated 95% CIs will be reported (using the cmh commonriskdiff (test=mh) option in SAS PROC FREQ). A similar 2x2x2x2x2 Cochran-Mantel-Haenszel (CMH) test will be used for EDP 235 [REDACTED] versus Placebo. There is no planned multiplicity control for the analysis of efficacy endpoints.

In addition to the summaries noted above, all data will be presented in listings. If the two EDP 235 treatment groups exhibit similar efficacy, a comparison may be done between the combined EDP 235 treatment groups and placebo.

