8.2.7. Change from Baseline in SARS-CoV-2 RNA Viral Load Assessed by RT-qPCR Through Day 33

The antiviral activity of EDP 235 on viral kinetics will be measured using SARS-CoV-2 RNA viral load assessed by RT-qPCR of NP swab samples on Days 1, 3, 5, 9, 14, and 33. Change from baseline values for SARS-CoV-2 RNA viral load will be summarized using the methods described in [Section 8](#).

8.2.8. Change from Baseline in Infectious SARS-CoV-2 Viral Load Assessed by Cell Culture Infectivity Assay Through Day 33

The infectious SARS-CoV-2 viral load will be measured using a SARS-CoV-2 cell culture infectivity assay of NP swab samples on Days 1, 3, 5, 9, 14 and 33. Change from baseline values for infectious SARS-CoV-2 viral load will be summarized using the methods described in [Section 8](#).

8.2.9. AUC of SARS-CoV-2 RNA Viral Load Assessed by RT-qPCR Through Day 33

The area under the curves (AUC) from Day 1 through Day 33 will be calculated for SARS-CoV-2 viral load data using actual sampling times via non-compartmental analysis using Phoenix[®] WinNonlin[®] Version 8.3.4 or higher according to the linear trapezoidal with linear interpolation

8.3.4. AUC of SARS-CoV-2 RNAemia Viral Load Through Day 33

The area under the curve (AUC) from Day 1 through Day 33 will be calculated for SARS-CoV-2 RNAemia viral load data using actual sampling times via non-compartmental analysis using Phoenix® WinNonlin® Version 8.3.4 or higher according to the linear trapezoidal with linear interpolation. AUCs will be derived for Days 1-14 and Days 1-33. Additionally, the AUC from Day 1 through Day 14 and the AUC from Day 1 through Day 33 will be standardized for 14 and 33 days by multiplying $14, 33/t_{last}$ where t_{last} is the actual time in days of the last available assessment. No AUC values will be calculated if there are less than 3 results available. The same methods used in [Section 8.2.9](#) will be applied.

8.3.5. Time to SARS-CoV-2 RNAemia TND Through Day 33

Time to SARS-CoV-2 RNAemia to TND is defined as per [Section 8.1.1.2](#) and will be summarized and analyzed as described in [Section 8](#).

8.3.6. Change from Baseline in SARS-CoV-2 Nucleocapsid Antigenemia Through Day 33

Change from baseline of SARS-CoV-2 nucleocapsid antigenemia will be summarized as described in [Section 8](#).

8.3.7. Proportion of Subjects with Positive SARS-CoV-2 Serostatus at Day 33

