 - If the day and month are missing or a date is completely missing, it will be considered as missing.

Imputation rules for SARS-CoV-2 viral load and SARS-CoV-2 nucleocapsid antigenemia data:

- SARS-CoV-2 RNA and RNAemia viral load values reported as TND will be imputed with 1 copy/mL (i.e., 0 log₁₀ copies/mL)
- Infectious SARS-CoV-2 viral load values reported as TND will be imputed with 1 TCID₅₀/mL (ie, 0 log₁₀ TCID₅₀/mL).
- SARS-CoV-2 nucleocapsid antigenemia reported as TND will be imputed as 1 fg/mL.
- Numeric values <LLOQ will be set to the LLOQ.
- Numeric values >ULOQ will be set to the ULOQ.
- Values reported as “POS” will be imputed as half of the LLOQ.
- Imputed values will be used in tables and listings will present actual data.

Imputation rules for PK concentrations

- Serum concentrations that are <LLOQ will be treated as zero for PK analyses, except for <LLOQ values observed between 2 quantifiable concentrations and <LLOQ values that occur after the first quantifiable point, which will be set to missing. If consecutive <LLOQ concentrations are followed by quantifiable concentrations in the terminal phase, those concentrations after <LLOQ concentrations will be treated as missing. Missing concentrations will be treated as missing in the PK parameter calculations.

Imputation rules for all other data:

- No other imputations will occur for any data not previously mentioned.

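### For secondary change-from-baseline endpoints, SAP Section 8 fixes neither the time point nor the governing test, and its ANCOVA ignores a subject's earlier visits when one is missed

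*SAP*

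**What the plan says.** Section 8 gives one recipe for all change-from-baseline endpoints: "For treatment comparisons of change from baseline endpoints, analysis of covariance (ANCOVA) models will include treatment group", the two stratification factors and the baseline value. Its output is described as follows: "The least-squares means, SE, and 95% CIs will be presented for individual groups and the difference between groups". A p-value accompanies that difference. The section then adds: "In addition, a two-sample t-test will be used to compare change from baseline between treatment without covariate adjustment (unadjusted mean difference"; this test has its own p-value under equal variances. It also asks for line graphs of adjusted and unadjusted means, and says openly that efficacy multiplicity is not controlled.

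The endpoint sections refer back to this recipe. Section 8.2.7 reads: "Change from baseline values for SARS-CoV-2 RNA viral load will be summarized using the methods described in" Section 8. Section 8.2.8 (infectious load) is worded in the same way, and Section 8.2.2 sends the symptom total score to the same place. All three run through Day 33 and none names a visit.

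Section 3.1 leaves missing data unimputed unless a rule says otherwise. The viral-load rules in Appendix 14.5 cover results that exist (TND, below or above the quantitation limits, POS), not samples that were never taken, and the appendix closes: "No other imputations will occur for any data not previously mentioned". The only sensitivity analysis stated (Section 8.1.2) is a per-protocol rerun of the primary efficacy endpoints.

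**The concern.** Two things are left open. First, a reader cannot tell which number answers the viral-load or symptom-score endpoint. Several time points, two doses and two unranked tests are all eligible, and the choice could be made after the results are seen.

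Second, an ANCOVA fitted at one visit uses only the subjects measured at that visit. A subject with Day 3 and Day 5 swabs but no Day 9 swab contributes nothing to Day 9, although the earlier values predict the missing one. If subjects with higher load or worse symptoms miss more visits, and more of them are on placebo, the placebo arm looks better than it was and the treatment difference shrinks.

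**Working it through.** **How the model is read.** The SAP does not say in words that the ANCOVA is fitted separately at each time point. Three features point that way: the model has no visit term, subject effect or covariance structure; Section 3 speaks of by-visit analyses; and adjusted means are drawn as lines over time.

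**Count of p-values.** Formula: post-baseline time points × contrasts with placebo × tests.

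- Contrasts: two doses, each against placebo (three arms, Section 2.1). Section 8 does not list the ANCOVA pairs; two is taken from its Cox paragraph.
- RNA load, Days 3, 5, 9, 14 and 33 (Section 8.2.7): 5 × 2 × 2 = **20**. Infectious load has the same visits and the same count.
- Total score at those five visits: **20**. With the Day 2 and Day 4 calls: 7 × 2 × 2 = **28**.
- Total score on every diary day, Day 2 to Day 33: 32 × 2 × 2 = **128**.
- With the optional pooled-dose contrast, 20 becomes 5 × 3 × 2 = 30 and 128 becomes 32 × 3 × 2 = 192.

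The SAP does not decide the time unit for the total score. Section 3 summarizes diary data by actual day; Section 8.2.2 mentions study visits, but only for the individual symptom scores.

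**What nominal means here.** The level is given as "a two-sided test will be used at a significance level (alpha) of 0.05 for all analyses". With no true effect, the expected number of results below 0.05 is 20 × 0.05 = 1.0, or 128 × 0.05 = 6.4. The chance of at least one, if tests were independent, is 1 − 0.95^20 = 0.64 or 1 − 0.95^128 = 0.999. The tests are correlated, so these are upper references. In simulation (70 per arm assumed, autoregressive normal data) the chance was 0.31 to 0.46 for 20 tests (correlation between adjacent visits 0.9 to 0.5) and 0.67 to 0.89 for 128 tests (0.95 to 0.8). The second test alone moves one contrast from 5% to about 6–8% (75 per arm assumed).

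**Missing visits.** The SAP gives no dropout rate, SD or effect size, so all inputs here are assumed: five visits, unit SD, adjacent correlation 0.7, true difference −0.50 SD, and dropout depending on the previous visit's value. Each row averages eight runs of 20,000 subjects per arm. The fit is an observed-case ANCOVA at the last visit, adjusted for baseline.

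| Log-odds of dropout per SD | Missing, placebo / active | Estimate |
|---|---|---|
| 0 | 11.4% / 11.4% | −0.499 |
| 0 | 34.3% / 34.3% | −0.504 |
| 0.5 | 12.7% / 10.2% | −0.495 |
| 1.0 | 16.5% / 10.8% | −0.483 |
| 1.5 | 22.1% / 12.8% | −0.457 |
| 1.5 | 31.0% / 19.1% | −0.441 |
| 1.5 | 46.0% / 30.7% | −0.420 |

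Unrelated missingness gives no material bias. Moderate to strong dependence gives about −0.48 to −0.42, a loss of 0.02/0.50 = 4% to 0.08/0.50 = 16%.

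A second simulation, in log10 units, had Day 9 missing in 11–16% of placebo and 5–7% of active subjects, driven by Day 5 load. A true −0.50 was estimated as −0.44 to −0.47 from observed cases and as −0.50 by a likelihood model using earlier visits. With values floored at TND = 0 log10 and 75 per arm, the full-data difference was −0.465; observed cases gave about −0.43 and the likelihood model about −0.46, with precision at least as good.

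**The case against.** Much of the case on the other side stands.

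- A reader might infer that the SAP prescribes a test on every diary day, hence 128 p-values. It does not say so. By-visit fitting is an inference, and 128 is only the upper end of a range that starts at 20.
- A reader might infer an uncontrolled familywise error. The SAP makes no familywise claim: it declares that multiplicity is not controlled, and these are secondary endpoints in a Phase 2 study whose primary objective is safety. The error rates above only show that the p-values need cautious reading.
- A reader might infer that efficacy has no governing estimate at all. Section 8.1 names two primary efficacy endpoints, one for symptoms and one for RNA, and Section 8.2.9 summarizes RNA load as an AUC. The gap is confined to the change scores.
- The t-test is introduced as an addition and labelled unadjusted, which suggests a supplementary role. That role is nevertheless not stated.
- The bias is hypothetical and runs towards no effect, so it would not create a false positive. Appendix 14.1 allows home visits and keeps subjects who stop treatment in follow-up, which limits missed visits. The likelihood model does well partly because the simulations let missingness depend on observed values, which is that model's own assumption.

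None of this says which visit or which test answers Sections 8.2.2, 8.2.7 and 8.2.8. Declaring no multiplicity adjustment does not settle that choice, and a separate AUC endpoint does not settle it for the change scores.

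**Conclusion.** The concern holds in a limited form. For the secondary change-from-baseline endpoints the SAP names no time point, does not rank its two tests, and uses a model that sets aside a subject's earlier values at a missed visit. Read by time point, this gives 20 p-values for RNA load and 20 to 128 for the symptom score, all nominal. The cost in bias is modest and conditional: about −0.42 to −0.48 for a true −0.50 under the assumed moderate to strong dependence, and none if missingness is unrelated to severity. The documents give no dropout rate with which to narrow this. A longitudinal likelihood model is the better method at little cost. That and a stated governing analysis carry the point; which visit is chosen, and whether t-test p-values are printed, do not.

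**What to change.** In Section 8, make one MMRM per change-from-baseline endpoint the governing analysis. Fit it over the scheduled post-baseline visits (Days 3, 5, 9, 14 and 33), with treatment-by-visit, baseline-by-visit, the two stratification factors and an unstructured covariance. Use the same days for the symptom total score: five visits need 5 × 6 / 2 = 15 covariance parameters, while 32 diary days would need 32 × 33 / 2 = 528. The other diary days can still be plotted.

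State before unblinding which visit contrast is the main one for each endpoint; the choice is the sponsor's. That leaves two main p-values per endpoint, one per dose. Label the by-visit ANCOVA and the unadjusted t-test as supportive.

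The cost is a few sentences in the SAP, some reprogramming and a visit chosen in advance. A normal model will fit less well at late visits where many values are TND and set to 0 log10, a limit the planned ANCOVA shares.
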